13.0 Recording with Audio, Video, or Photographs

This study may optionally involve recording video and/or taking photographs of participants performing tasks. If participants agree (on the Informed Consent Form) to have these collected, digital videos and/or photographs would be used for educational, reporting, or illustration purposes and will be stored for at least 3 years after closure of the protocol. The Principal Investigator (PI) will store these digital media files on their password-protected computer, and no other study team members will have access.

14.0 Potential Benefits to Participants:

There are no direct benefits to the participants participating in this research. The results may help better inform future research on how CES may influence sympathetic nervous system responding under conditions of stress.

15.0 Risks to Participants:

We anticipate three primary risks:

1. Cutaneous Irritation due to StressX Belt: Mild electrical shock to the torso is commonly used as an effective, safe method of inducing acute stress in a laboratory context. The StressX Pro Belt meets strict safety regulation standards set forth by the International Electro Technical Commission (document IEC 479-2:1987). Specifically, an excess of 5000mJ of transient or capacitive discharge is required to produce direct serious health risk and the electrical stimulus system in the study (SETCAN StressX Pro Belt) has a maximum output of 92mJ (< 1mA over 150ms), more than 98% lower than the threshold to cause health risk (IEC 479-2: 1987). The shocks we deliver will be unpleasant but not painful, set to intensity level 3 (of 5) which delivers shock for only 60-80ms. In our recently completed study (DEVCOM AC IRB protocol 18-007), we completed over 100 sessions using this shock belt, with over 1,000 shocks delivered on (self-selected) intensity levels 1 through 3. With these settings, only one participant reported mild skin irritation, which the AC IRB determined did not qualify as an UPIRTSO. In the present study, we will use a fixed shock intensity of 3; while low probability (we estimate 1-2% incidence given our prior study), if at any time a participant can no longer tolerate the shock (either psychologically, or they experience anything more intense than mild skin irritation), we will reschedule their session. See Study Withdrawal Guidelines (Section 3.0) for details. Participants will be informed of shock belt-related risk, and that they can opt-out at any time, in the Informed Consent Form.
2. Side Effects due to CES Administration: Cranial electrotherapy stimulation (CES) has very low incidence of side effects; when they do occur, they tend to include transient dizziness, vertigo, headache, nausea, tinnitus, lightheadedness, or skin irritation under the electrodes. The manufacturer of the Alpha-Stim AID (EPII) suggests that side effects are seen in less than 1% of people using the device, and they are “all mild and self-limiting.” To gain a

more objective assessment, we reviewed some CES studies that were not associated with (i.e., funded by, conducted by) the manufacturer. In one of the largest CES studies to date, none of the 115 participants (N = 60 in Active CES group) reported any side effects with six weeks of daily (one hour per day; 0.5Hz at 100 μ A) CES administration (Barclay & Barclay, 2014). In another similarly designed study using CES at 0.5Hz and 300 μ A, 3 of the 12 participants dropped out of the study due to mild side effects (2 with dizziness, 1 with headache) (Bystritsky et al., 2008). In another study, participants receiving Active CES treatment for 2 weeks (20 minutes per day; N = 7; 2mA at mixed frequencies) showed similarly low rates of reported side effects as the Sham CES group (McClure et al., 2015). In our own recent study (0.5Hz, 100 μ A), reports of side effects were also no more frequent in the Active versus Sham CES group (Brunye et al., 2022). Given these results, we estimate that the rate of side effects with our proposed design will be very low (i.e., less than 25%), especially given our individualized daily thresholding procedure. See Study Withdrawal Guidelines (Section 3.0) for details. Participants will be informed of the risk of CES side effects, and that they can opt-out at any time due to discomfort with CES administration, in the Informed Consent Form.

3. Psychological distress due to rifle marksmanship: During the baseline and follow-up sessions, participants will use a simulated rifle to shoot targets in virtual reality. This is like a first-person shooter video game, which research shows can variably activate positive (i.e., reward; Koepp et al., 1998) or negative (i.e., sadness; Ravaja et al., 2008) emotions. There are vast inter-individual differences in the emotions experienced during or after video game play (Avila et al., 2008; Ravaja et al., 2008), making it difficult to predict which individuals will experience positively versus negatively valenced emotion. While we believe the risk of psychological distress due to this experience is low, it is possible that participants will experience distress during or after the rifle marksmanship task (such as sadness, remorse, fear, or anxiety). It is unknown whether the rate of distress will be higher or lower in civilians versus military personnel; it is also unknown whether the rate of distress will be higher or lower in participants with prior video game experience (i.e., evidence for desensitization in this manner is equivocal; Regenbogen et al., 2010). Most importantly, if any participants report negative emotion to the research team, we will refer Soldier participants to the Office of Medical Support and Oversight (OMSO) at the DEVCOM Soldier Center, refer Tufts University student participants to the Tufts University Health Service, and recommend other participants (non-Soldier, non-Tufts affiliated) to speak with a qualified mental health practitioner.

We have no reason to believe that the acute stress response will differ between military personnel and civilian participants. In fact, research suggests that military personnel do not necessarily show higher levels of resilience to stress than civilians (Sohail & Ahmad, 2021). Furthermore, the primary population of military personnel recruited for this study (human research volunteers) has very limited military experience; furthermore, many will have a military occupational specialty (MOS) that is not infantry (e.g., engineer, aviation, transportation, maintenance), and most (if not all) will have never been deployed outside of the US or experienced combat. For these reasons, we do not have any compelling reason to believe they will have higher resilience to acute stress relative to civilians.

We do not anticipate any issues with virtual reality sickness/simulator sickness given that there is no virtual movement or optic flow through the virtual environment. Rather, participants are stationary in the environment; indeed, in our recently completed protocol, we experienced no reports (in over 200 sessions) of any typical symptoms of simulator sickness (e.g., nausea, headache).

If at any time, a **civilian** participant feels that they have been injured by the shock belt or CES and needs emergency care, Emergency Medical Care will be provided by calling 911, consistent with the Tufts University emergency response. It cannot be determined in advance which hospital or clinic will provide care. The participant and/or their insurance will be responsible for medical expenses.

If at any time, a **Soldier (i.e., DOD healthcare beneficiary)** participant feels that they have been injured by the shock belt or CES and needs emergency care, Emergency Medical Care will be provided by calling 911, consistent with the Tufts University and DEVCOM Soldier Center emergency response. This care includes but is not limited to free medical care at Army hospitals or clinics.

16.0 Withdrawal of Participants:

As in all human use protocols, participants will be fully briefed on the purpose, risks and procedures of the study before being asked to participate; they will also be informed of their right to withdraw from the study at any time without prejudice. During all sessions, participants will be allowed to stop participation at any time if they experience any side effects (or for any other reason).

As detailed in Section 3.0, we will also withdraw participants from the study based on several criteria (see Appendix E for flowchart). All data collected up to the point of withdrawal will be destroyed and not analyzed.

17.0 Data Management and Confidentiality:

All data and personal information obtained during this protocol will be considered privileged and held in confidence. Each participant will be assigned a unique subject ID number. This subject ID number will not contain any personal identifiers such as: name, social security number, address, date of birth, zip code, etc. This subject ID number will be the only identifier on all data collection instruments (i.e. questionnaires, collection forms, data files, and computer records), and used during data collection and analysis. Only the study investigators will have access to the Informed Consent Forms containing participant names and signatures. A master list linking the participants' personal identifiers with the study participant ID number (i.e., a link) will be kept as an electronic document on a password-protected government computer.

Only the PI will have access to the master file (link). Associate investigators and study staff will have access only to the coded data and not to personally identifiable information. The document that links participants' names to their ID number will be kept for three years after closure following verification and validation of the data, when it will be destroyed. The Informed Consent Forms will be destroyed three years after the study is closed. When the results of this protocol are published or disseminated in any manner,

no information will be included that could reveal identity. Complete confidentiality cannot be promised to military participants because information bearing on the military participants' health may be required to be reported to appropriate medical or command authorities.

Data will be backed-up after each session and inspected by a member of the research team. All data and personal information obtained during this protocol will be considered privileged and held in confidence. Each participant will be assigned a unique subject ID number. This subject ID number will not contain any personal identifiers and will be the only identifier on all data collection instruments (i.e. questionnaires, collection forms, and computer records). Furthermore, when the results of this protocol are published or disseminated in any manner, no information will be included that could reveal identity.

Participants will complete all questionnaires via Qualtrics, which is GDPR (General Data Protection Regulation) compliant, and/or tablet computers running a local software package (e.g., PsychoPy, SuperLab, or custom C# software). All data will be coded, with the only identifier being the participant's participant ID number assigned at the beginning of the study. Access to Qualtrics data is secure and individual permissions set prior to the study with access privileges. Once data have been processed, organized, and provided to the researchers from both Qualtrics and tablet interfaces, all electronic locally stored data will be deleted.

The Informed Consent Forms and any paper copies of the collected data will be stored in a locked file cabinet in the Principal Investigator's office (DEVCOM SC, [name]) for at least 3 years after closure of the protocol. Data will be transferred via DOD SAFE, OneDrive, and/or locally approved electronic data transfer sites or cloud applications to password-protected computers or held on secure, password-protected servers and hard drives for subsequent data analysis. Once the protocol is complete, data will be verified and archived to a storage medium (e.g. approved data repository or encrypted hard drive) or in the case of hard copies stored in locked file cabinets at the Soldier Center for at least 3 years after closure of the protocol. This data will not contain identifying information.

18.0 Provisions to Protect the Privacy and Confidentiality of Participants and the Research Data:

Participants will be informed of the possibility of future use for the data that is collected as part of the consenting process. Data files may also be shared with other government and non-government collaborators and contractors for future use.

The data collected in the current study will be used in future studies. There is a statement in the Informed Consent Form to obtain consent for future use of the data collected. Consent to future use of all data collected will be required for participation in the current study and is included under the inclusion criteria.

Participants in this study will consent to allowing their samples to be saved for future research that may or may not be directly related to the hypotheses set forth in this protocol. Therefore, once the protocol is closed, samples will be retained for future analyses that may or may not align with the aims set forth in the present protocol. In addition, the data may be used as inputs for developing models to assess measures of

performance, readiness, recovery, and/or lethality at the individual, small unit and platoon-level. DEVCOM Soldier Center or other approved entity may employ a machine learning framework within the database to identify groups of individuals who show an outcome of interest, and untargeted analysis will search for a set of dependent measures that are sensitive to conditional changes (i.e., with versus without an environmental stressor). In addition, machine learning algorithms may be used to down-select dependent measures that correspond to other classification standards.

In all cases, future use of data collected as part of this protocol will be restricted to deidentified data after the master linking document (linking participant identity to participant ID) has been destroyed.

19.0 Provisions to Monitor the Data to Ensure the Safety of Subjects:

The PI will periodically inspect the data, especially the CES side effect questionnaire responses, to ensure that research staff are following all mitigation procedures outlined in this protocol.

20.0 Compensation for Research-Related Injury:

There will be no financial compensation offered for research-related injury.

21.0 Data Sharing and Specimen Banking:

See Section 18.0.

22.0 International Research:

N/A

23.0 Multiple sites:

This study is a collaboration between the Center for Applied Brain and Cognitive Sciences (CABCS) at Tufts University (Medford, MA) and the DEVCOM Soldier Center (Natick, MA). Following initial and continuing Tufts University IRB approvals, the research team will electronically transmit all study protocol documents to the DEVCOM Soldier Center HRPP office and seek secondary Human Research Protections Office (HPRO) approvals prior to commencing participant recruitment or any other study procedures. Any modifications required by the Soldier Center HRPO to secure concurrence will be submitted in an amendment to the Tufts University IRB. The PI will be responsible for sharing (via email) the most recent protocol, approvals, and consent documentation. Any modifications will be done through the Tufts University IRB and be communicated to the Soldier Center HRPO, in accordance with institutional agreements. The PI will closely monitor research staff progress at both data collection sites.

24.0 Reliance Agreements/Single IRB:

The Tufts University IRB will serve as the IRB of record.

25.0 Qualifications to Conduct Research and Resources Available:

Because we recently completed data collection on a very similar study (DEVCOM Armament Center IRB #18-007), research assistants have been trained by project investigators on the execution of all tasks. Furthermore, investigators attended a virtual training seminar offered by the manufacturer of the Alpha-Stim AID device (EPII), which included practical and safety-related topics for the effective use of the device.

All study personnel have completed CITI training required for social and behavioral research. The PI, [name] is a Cognitive Neuroscientist and Principal Investigator at the Tufts Center for Applied Brain and Cognitive Sciences, and has over 10 years of research experience planning, conducting, and managing research in the cognitive sciences. She holds a PhD from Tufts University in Cognitive Neuroscience and completed post-doctoral training at Massachusetts Institute of Technology (MIT). At CABCS, she successfully manages the execution of large-scale research projects involving data collection from neurophysiological and physical sensors and has substantial experience applying advanced analytical approaches to multimodal data streams.

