Exclusion Criteria: The following exclusion criteria will be evaluated by self-report (on the Informed Consent Form) prior to beginning the study.

1. Use of prescription medications, other than oral contraceptives, as they may alter stress hormones (Granger, Hibel, Fortunato, & Kapelewski, 2009).
2. Women only:
 - a. Pregnant or plan to become pregnant during the study, as the shock belt may be unsafe for pregnant women and their children.
 - b. Nursing, as it may alter stress hormones (Ahn & Corwin, 2015).
3. History of:
 - a. A neurological or psychological disorder (such as depression, anxiety disorders, migraines, cluster headaches, seizures, Post-traumatic stress disorder (PTSD) or panic attacks). Individuals with neurological and psychological disorders may exhibit altered stress responses, not representative of the population (Spijker & van Rossum, 2012).
 - b. Cardiac disease (including arrhythmia or fast or skipped heart beats). The shock belt may be unsafe for individuals with cardiac disease (Steptoe & Kivimäki, 2012)
 - c. Implanted medical devices, such as pacemakers. The Shock belt may be unsafe for individuals with an implanted medical device.
 - d. Hypertension. The Shock belt may be unsafe for individuals with diagnosed hypertension (Spruill, 2010). This risk is low, and the prevalence of undiagnosed hypertension in our targeted cohort (ages 18-40) is also very low; for these reasons, we believe self-report of diagnosed hypertension is sufficient.
 - e. Insomnia, as insomnia is associated with chronic physiological arousal (Bonnet & Arand, 2010)
 - f. Head injury (including neurosurgery, concussion, TBI, skull fracture, hematoma)
 - g. Illness that caused brain injury
 - h. Any other brain-related condition (such as traumatic brain injury)

- i. Metal in the head (outside of mouth, such as shrapnel, surgical clips, or fragments from welding or metalwork)
- j. Implanted medical device (e.g., pacemaker, insulin pump)

Study Withdrawal Criteria:

We have five study withdrawal criteria, related to minimum CES intensities, failing to meet minimum performance during the criterial learning tasks, intolerance for torso shock, self-reported symptoms on the Daily Participant Questionnaire (Appendix A), and intolerance for CES.

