First, during the individualized baselining phase (part of the Thresholding and Baselining session), if a participant does not reach our minimum CES intensity of 250µA (i.e., a 300µA minimum threshold), they will be dismissed from the study.

Second, during the baseline or follow-up session, if a participant cannot reach the accuracy criterion during the criterial learning tasks within 5 study-test cycles, they will be dismissed from the study.

Third, during the baseline or follow-up session, if a participant cannot tolerate the torso shock (psychologically or physically), we will reschedule their session for a different day. If during two consecutive sessions they cannot tolerate the level 3 intensity, they will be dismissed from the study.

Fourth, at the beginning of any CES session, if the participant answers a 3 or higher (on the scale from 1-4) to any of the Daily Participant Questionnaire items, their session will be rescheduled for a different day. If they report 3 or higher for any of these questions for two consecutive sessions, they will be dismissed from the study.

Fifth, during any CES session, if a participant cannot tolerate the CES administration at their individualized intensity (i.e., answering ≥ 3 to a single item on the “presence and intensity” *and* “relation to stimulation” sections), they will receive secondary CES stimulation as described in the Procedures section (6.0). If their reported symptoms do not successfully subside (i.e., falling below a 3 rating) after the secondary stimulation, and this occurs for two consecutive sessions, they will be dismissed from the study.

Each of these study dismissal criteria are described in more detail in the Procedures section (6.0), and detailed in the Appendix E flowchart.

4.0 Special Populations:

- Children
- Fetuses/Neonates
- Prisoners
- Members of the military
- Non-English speakers
- Those unable to read (illiterate)
- Employees of the researcher
- Students of the researcher

- Adults lacking capacity to consent and/or adults with diminished capacity to consent, including, but not limited to, those with acute medical conditions, psychiatric disorders, neurologic disorders, developmental disorders, and behavioral disorders
- Disadvantaged in the distribution of social goods and services such as income, housing, or healthcare
- Fear of negative consequences for not participating in the research (e.g. institutionalization, deportation, disclosure of stigmatizing behavior)

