5.2 Sample Size

Sample size estimation was based on effect sizes from Barclay & Barclay (2014) who found that CES reduced subjective anxiety with an effect size of $f = 0.47$. Using GPower, the total sample size was estimated to be 38 to achieve power of 0.80 with an alpha criterion of 0.05. Our goal is therefore 40 complete data sets, with 20 participants in each of the two groups.

6.0 Procedures Involved:

We will use a double-blind, placebo-controlled design with random assignment of participants to one of two experimental groups: Active versus Sham CES. Two versions of the critical learning and virtual reality tasks have been developed (Brunyé & Giles, 2023; used in DEVCOM Armament Center IRB protocol 18-007, Tufts University protocol 1808016), and will be used herein, in balanced order across participants.

Military participants will be transported to and from the CABCS research performance site in Medford, MA, for participating in the baseline and follow-up session. If overnight accommodations are required for Soldiers, those will be provided along with other travel related items (e.g., per diem). Travel will be planned by the research team and coordinated with unit leadership (if troop request) or HRVPO (if HRVs). Civilian participants will not be provided with transportation, accommodations, or any other travel-related compensation.

All non-disposable devices used in the protocol will be disinfected in accordance with Occupational Health and Safety Administration and Centers for Disease Control

guidance, and product label instructions, paying attention to the required personal protective equipment and the contact time needed to achieve disinfection. In addition, all frequently touched surfaces in the research area, such as workstations, countertops, and doorknobs will be cleaned between participants.

Upon scheduling, participants will be randomly assigned to the Active or Sham CES condition, using the [=rand()] function in Microsoft Excel. All participants will complete a Thresholding & Baseline session, the CES administration sessions, and then a Follow-up session.

Testing Day 1: Thresholding & Baseline

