1. Active or Sham CES Administration: Participants will be asked to continue sitting and relaxing in the chair and the electrode cable (still attached to their earlobes) will be connected to a different CES device. Two types of CES devices will be used: an Active device or a Sham device. The Sham devices are manufactured by EPII and look and behave exactly like the Active devices, however they do not actually send any electrical current to the electrodes. The two versions of the devices will be coded as devices A and B, and neither the experimenter nor participant will know which is Active and which is Sham; only the Principal Investigator will keep the key to decode whether the device is Active or Sham, to be revealed only during data analysis (or to a medical professional if there is an adverse event). The experimenters and participants will only know which coded device (device A or B) to use during CES sessions. In both conditions, the device will be powered on and set to the intensity identified during the CES Individualized Thresholding phase, and a countdown timer (displayed on the device screen) will begin.

After the 20 minutes of stimulation have elapsed, the device will automatically turn off. Immediately after the 20-minute CES administration, participants will complete the STAI-S questionnaire a second time, and the CES side effects questionnaire.

2. CES Secondary Administration: If a participant answer is ≥ 3 to one or more questions on the CES side effects questionnaire (in *both* the “presence and intensity” and the “relation to stimulation” sections), we will follow the manufacturer’s guidelines to administer additional CES until symptoms subside. According to the manufacturer’s internal research (derived from an analysis of over 10,000 CES sessions), brief secondary CES administrations can help

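### Section 16.0 destroys all data from participants withdrawn under Section 3.0, so the retained side-effect ratings omit anyone dismissed for persistent CES intolerance

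*Protocol*

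**What the plan says.** Protocol Section 3.0, under Study Withdrawal Criteria, begins: "We have five study withdrawal criteria". They concern minimum CES intensity, the learning criterion, tolerance of the torso shock, the daily questionnaire and tolerance of CES. On the last, a participant whose symptoms do not subside is covered by this rule: "after the secondary stimulation, and this occurs for two consecutive sessions, they will be dismissed from the study".

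Section 16.0 refers back to those criteria and then says: "All data collected up to the point of withdrawal will be destroyed and not analyzed". It makes no exception for side-effect ratings, Baseline values or reasons for withdrawal.

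On timing, Section 6.0 says: "Upon scheduling, participants will be randomly assigned to the Active or Sham CES condition". Of the Sham devices it says that "they do not actually send any electrical current to the electrodes", and of the blinding that "only the Principal Investigator will keep the key to decode whether the device is Active or Sham".

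The SAP compares Active with Sham across Baseline and Follow-up. It names no analysis set, does not mention withdrawals and plans no side-effect analysis.

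**The concern.** Every withdrawal criterion acts after randomisation, and some act once the allocated treatment has begun. The intolerance rule is the critical one. It removes people for symptoms that they attribute to stimulation, in a trial where only one arm receives current. Section 16.0 then deletes the ratings that led to the dismissal.

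Two things are at stake. The first is tolerability: the study collects side-effect ratings after every CES session at intensities above those of the group's previous study, yet the surviving ratings would come only from people not withdrawn. The second is the description of selection. The efficacy comparison becomes completers only, and without the Baseline values of those who left, nobody can show whether the two arms lost similar people.

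**Working it through.** **The plan's own figure.** For two groups with f = 0.47 and alpha 0.05, the noncentral F test (df 1 and N-2, noncentrality f²N) gives power 0.805 at N = 38 and 0.826 at N = 40. The stated total of 38 reproduces and is not in question.

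**When each rule acts** (Sections 3.0 and 6.0):

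| Rule | When | Relation to allocated CES |
|---|---|---|
| Minimum intensity | Thresholding, Day 1 | Before; everyone is tested on one active device |
| Learning criterion | Baseline or Follow-up | Before, or after the CES sessions |
| Torso shock | Baseline or Follow-up | Before, or after the CES sessions |
| Daily questionnaire | Start of a CES session | Sometimes before any allocated CES (first two attempts), otherwise after it has begun |
| CES intolerance | During CES sessions | During |

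Thresholding and Baseline dismissals should differ by arm only by chance. The others may differ systematically, and the intolerance rule most obviously so. Someone dismissed at Follow-up could lose the ratings from all 20 sessions.

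**How many people.** Section 3.0 anticipates 40-50% attrition and a target of 40 complete data sets.
- Entrants: 40/(1 - 0.40) = 66.7, about 67; 40/(1 - 0.50) = 80.
- Losses: 67 - 40 = 27; 80 - 40 = 40.

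So 27-40 is an upper figure, reached only if every loss counts as withdrawal under Section 16.0. The share lost after CES begins is not stated. If it were 25%, 50% or 75% (assumed), that would be 7-10, 13-20 or 20-30 people.

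**Side effects.** Section 15.0 gives two reference points. At 100 µA, "none of the 115 participants (N = 60 in Active CES group) reported any side effects": 0/60 Active, exact (Clopper-Pearson) 95% interval 0 to 6.0%. At 300 µA, "3 of the 12 participants dropped out of the study due to mild side effects": 25%, interval 5.5% to 57.2%. Neither is a dismissal rate for this trial, which requires persistent symptoms in two consecutive sessions, generally at 50 µA below threshold. Taking 5%, 10% or 25% of Active starters dismissed for intolerance (assumed), with 20 completing and no other loss:
- 20/0.95 = 21.1 starters, 1.1 dismissed
- 20/0.90 = 22.2 starters, 2.2 dismissed
- 20/0.75 = 26.7 starters, 6.7 dismissed

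In each case the retained ratings include none of those dismissed.

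**Efficacy, illustration only.** Assume a proportion p lost from Active only, no true CES effect, and correlation r = 0.3 to 0.5 between intolerance and change in outcome. Bias in SD units = r × φ(z)/(1 - p), with z the upper-p normal quantile. For p = 0.10 and r = 0.5: 0.5 × 0.1755/0.90 = 0.097. Type I error is for a two-sided 5% t-test on change with 20 per arm (100,000 simulated trials).

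| p | Bias (SD) | Type I error |
|---|---|---|
| 5% | 0.03-0.05 | 5.0-5.4% |
| 10% | 0.06-0.10 | 5.4-6.2% |
| 25% | 0.13-0.21 | 6.7-10.5% |

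If both arms lost the same proportion through the same selection, the bias would be zero.

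**The case against.** Several counter-arguments carry weight.

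- *Side effects are not a planned outcome.* They are not among H1 to H4, and the SAP does not analyse them. This stands, and it limits the reach: no planned test is distorted, only a later statement about tolerability.
- *Information may survive elsewhere.* Section 17.0 keeps the identity link for three years after closure and the Principal Investigator holds the device key, so counts by arm could probably be rebuilt. Section 19.0 has the Principal Investigator inspect side-effect responses. But that inspection serves to check staff procedure, and no text requires counts to be reported. A reader might infer that intolerance must be under-counted whatever its true rate. That goes too far: it ignores surviving counts, and a true rate of zero would leave nothing to miss.
- *Some rules should rarely act.* Section 6.0 reports that all participants in the previous study met the learning criterion within three cycles, and Section 15.0 expects shock problems in 1-2%. This stands.
- *Keeping the data would not settle selection.* With 20 completers against 2 or 7 non-completers, a Baseline comparison has 80% power only for differences of about 2.2 or 1.3 SD. It can be descriptive only.

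Three further inferences are tempting. A reader might conclude that the cited 300 µA study would have kept 9 people and no side-effect drop-outs under this rule. That assumes voluntary drop-outs are covered, which the protocol leaves unclear. A reader might take the cap of 100 enrolled to mean 60 people's data lost; that needs 60% attrition, above what Section 3.0 anticipates. A reader might also conclude that the efficacy result is biased towards Active. The documents give neither the dismissal rates by arm nor their relation to outcome, so neither direction nor size follows.

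**Conclusion.** The concern holds and should be fixed. The firm part needs no assumed rate: taken literally, Section 16.0 leaves no side-effect ratings from anyone dismissed for persistent CES intolerance, and no Baseline values from anyone withdrawn under Section 3.0. If intolerance dismissals occur, a tolerability statement from the retained data would be too favourable.

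The efficacy part is weaker. The comparison is completers only, and selection by arm cannot be described from Baseline values. Any resulting bias is negligible under the assumed inputs at 5-10% Active-only loss and material only near 25%, a rate that the two-session rule makes less likely.

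At most about 27-40 people's data are at risk, an unstated share of them dismissed before any allocated CES. Two points of scope remain open. Six-week removal (Section 6.0) is not one of the five criteria. Voluntary stopping is described in Section 16.0, but whether the destruction sentence covers it is not said. The consent form and the Appendix E flowchart were not available to this review.

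**What to change.** 1. Replace the destruction sentence in Section 16.0 with: *Data collected up to withdrawal will be retained and analysed unless the participant asks for their destruction.* State whether six-week removal and voluntary stopping count as withdrawal, and align the consent form if needed.
2. Report by arm: the numbers randomised; withdrawals with timing and reason; side-effect ratings for everyone with at least one CES session, including those dismissed for intolerance; and a descriptive comparison of Baseline values between completers and non-completers.

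A mixed model using all available data may be added as a sensitivity analysis but is not required. Where loss depends on the change itself, and with an assumed Baseline to Follow-up correlation of 0.5, it still leaves 0.10-0.16 of the 0.13-0.21 SD bias at 25% loss, about three-quarters.

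The cost is a short amendment, one extra table, and a consent-form edit or re-consent if participants were promised destruction. The consent to future use in Section 18.0 does not settle that. Data already destroyed cannot be recovered; for those participants, report whatever counts and reasons survive. The withdrawal rules and the sample size do not change.
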